5.1.1 Preparation criteria applying to both treatment arms

The following criteria apply to all study RBC units in both treatment arms. Any study RBC unit which does not meet all these criteria will be considered a protocol violation.

1. Institutional processing standards will be maintained for all units.
2. All study RBC units should be pre-storage leukoreduced.
3. All study RBC units should be stored in either AS1, AS3, or AS5.
4. No study RBC unit should be washed before release from the transfusion service.
5. No study RBC unit should be volume-reduced.
6. No study RBC unit should include a frozen product.
7. No study RBC unit should be deglycerolized.
8. No study RBC unit should be irradiated.

5.1.2 Preparation of RBC units for subjects randomized to receive units stored \leq 10 days

All study RBC units released from the blood bank for subjects randomized to receive units stored \leq 10 days should have been stored \leq 10 days at the time of transfusion.

If there are not enough suitable units stored \leq 10 days at the time a study RBC transfusion is needed, the blood bank should release suitable units with the minimum available storage time. The transfusion itself should not be cancelled or postponed because there are not enough suitable units stored \leq 10 days.

Study units stored longer than 10 days will be considered protocol deviations for subjects in this treatment arm if used for an outpatient transfusion and after the first successful randomization.

Subjects randomized to this treatment arm are likely to receive units with shorter storage times than the units they would receive if not in the study, but this is not guaranteed to be true for any particular subject.

5.1.3 Preparation of RBC units for subjects randomized to receive units stored \geq 30 days

All study RBC units released from the blood bank for subjects randomized to receive units stored \geq 30 days should have been stored \geq 30 days at the time of transfusion.

If there are not enough suitable units stored \geq 30 days at the time a study RBC transfusion is needed, the blood bank should release suitable units with the maximum available storage time. The transfusion should not be cancelled or postponed because there are not enough suitable units stored \geq 30 days.

Units stored less than 30 days will be considered protocol deviations for subjects in this treatment arm.

5.2 Administration

RBC units will be administered according to local institutional policy and safety standards as ordered by the medical team for patient care needs.

5.3 Concomitant Treatments

Standard medical care according to the local institutional standard will be provided to the subject.

6. SCHEDULE OF MEASUREMENTS

6.1 Red Cell Unit Sample Collection:

2 ml blood from each donor unit will be obtained from 6 sterile unit links/segments on the day of the 3 randomized outpatient transfusion events. PE and PS exposure, and microparticles, will be measured by flow cytometry using the LSR2-green, and all flow analyses will be recorded using FACSDiVa software. The plasma fraction from each red cell unit will be diverted to EPR (Bruker Elexys X-band system, Billerica, MA, USA), a Bio-Plex cytokine assay kit (Bio-Rad Laboratories), and a fluorescent immunoassay (DxFerr kit) to quantify concentrations of free heme/hemoglobin, cytokines (IL-1, IL-6, IL-8, MCP-1), and NTBI, respectively.

6.2 Patient Sample Collection (Table 1):

A. One - *four weeks prior to the first transfusion*:

- 15ml whole blood for flow cytometry and EPR measurements

B. *Immediately prior to each red cell transfusion*:

- 15ml whole blood for flow cytometry and EPR measurements
- 15ml to McLendon Labs
- blood culture to McLendon Labs (8-10ml blood/culture bottle)
- urine to McLendon Labs (12 ml urine)

C. *Two hours after each red cell transfusion (1 ½- 3 hours)*

- 15ml whole blood for flow cytometry and EPR measurements
- 15ml to McLendon Labs

D. *1 day after each red cell transfusion (about 21-27 hours after)*

- 15ml whole blood for flow cytometry and EPR measurements
- 15ml to McLendon Labs

E. *2 weeks after each red cell transfusion (+/- 2 days)*

- 10ml McLendon Labs

Patient Sample Processing: Blood will be obtained by port or peripheral access as available. Patient white cells will be isolated with established Ficoll separation techniques.. White cells will be tested by flow cytometry as above for key markers of activation (macrophages: CD62L, CD64, CD80, CD86, Tim1, neutrophils: The plasma fraction from each sample will be diverted to EPR (Bruker Elexys X-band system, Billerica, MA, USA), a Bio-Plex cytokine assay kit (Bio-Rad Laboratories), and a fluorescent immunoassay (DxFerr kit) to measure concentrations of free heme/hemoglobin, cytokines (IL-1, IL-6, IL-8, MCP-1), and NTBI, respectively. Clinical measurements obtained from patients will also include: CBC (4ml EDTA), reticulocyte count (4ml EDTA), HbS% (3ml EDTA), haptoglobin (1ml red top), chemistry labs (ferritin (0.5ml red top), iron saturation (1ml red top), lactate dehydrogenase (1ml red top)), urinalysis (12 ml) and blood culture (8-10ml/bottle). These clinical labs will be measured at intervals specifically defined in **Table 1**. Individual human samples of plasma and RBC will also be sent to [name] at the University of Colorado Denver to measure lipid metabolites and metabolomic profiles pre vs. post transfusion as an additional exploratory goal of this trial. The laboratory of [name] and his representatives will be receiving 30-200 individual samples of plasma and RBCs for this purpose. All samples will be de-identified.

6.3 Patient Clinical Outcomes:

A daily pain diary will be used and subjects will rate their pain on a ordinal numeric pain rating scale (0-10), indicate whether the pain was consistent with a “crisis,” indicate whether they utilized a healthcare facility, and record the amount of opioids used. Infection symptoms will also be documented daily along with the type, duration, and dose of any antibiotics taken if applicable. Subject ED and hospitalization events, and etiologies (see *definitions in 6.7*), will be recorded at regular intervals by the study coordinator during the study period using the available electronic medical record. Of note, diary completeness will be assessed at each face-to-face visit.

6.4 Patient Physical Exam:

Prior to each randomized transfusion, the PI or appropriately trained designee will perform a basic assessment of the patient. This exam will include a basic interval history (including review of any ED or hospital visits), a focused review of systems, and a focused physical exam.

Table 1: Schedule of Measurements

Study Measure	Daily	1-4 weeks pre-transfusion	Pre-every transfusion	2hr post every transfusion	24 hr post every transfusion	2 weeks post every transfusion	End of Study
Physical exam							
AE assessment							
Med assessment			X				X
CBC w/ differential*			X		X	X	
HbS%			X		X	X	
Blood culture			X				
Urinalysis w/ reflex culture			X				
Haptoglobin			X	X	X		
Plasma Hemoglobin			X	X	X		
Basic Metabolic panel [†]			X				
Ferritin & Iron Panel [#]			X	X	X		
Lactate dehydrogenase			X	X	X		
HS-CRP			X	X	X		
RBC Unit blood donor sample			X				
Flow cytometry sample		X	X	X	X		
Study Diary	X		X			X	X

*WBC, RBC, Hgb, Hct, Plt ct

[†]Creatinine, Bicarb, Chloride, BUN, Potassium (K), Sodium (Na), Glucose, Calcium

[#]Iron, Transferrin, TIBC, % Saturation

Table 2: Lab Sample Type and Storage Conditions

Blood Samples	Sample required	Tube type	Storage	Processed By
Red cell units	6 unit segments	NA	Room temp	PI or designee
Flow	8ml	Green top	Room temp (cold after 30 minutes)	PI or designee
Flow/EPR Labs	10 ml	Cytochex	Room temp	PI or designee
Hematology Labs	10 ml	EDTA	Room temp	McLendon Labs
Chemistry Labs	5 ml	Red top	Room temp	McLendon Labs
Microbiology Blood Culture	10 ml	Culture vial	Room temp	McLendon Labs
Microbiology Urine Culture	12ml	Sterile cup	Room temp	McLendon Labs

6.5 RBC Transfusions

The following data will be collected for each RBC unit ordered for the subject while on study:

- Unit ID number
- Source of unit (apheresis or whole blood collection)
- Blood group of unit (ABO and Rh)
- Leukoreduction status
- Irradiation status
- Volume reduction/washed unit status
- Storage medium (AS1, AS3, or AS5)
- Antigens matched (D, Cc, Ee, Kk, or other)
- Collection or expiration date (specifically recorded by the blood bank to maintain study coordinator blinding)
- Start time and end time of transfusion

6.6 Unblinding

Investigators will remain blind to treatment assignment until the entire study is complete. Only the DSMB, blood bank staff, and the designated study statistician at Medical College of Wisconsin should be aware of the treatment that is assigned to each subject. Unintentional unblinding of study participants will not be a reason for study discontinuation. Adverse events or urgent clinical care may lead to study termination as documented in section 6.7.

6.7 Ending of Study Participation

- 1) The subject completes the 3 transfusions
- 2) The subject decides to withdraw from the study
- 3) The subject moves away, dies, or is lost to follow-up
- 4) The patient no longer needs outpatient red cell transfusions as determined by the patient's provider
- 5) Subjects may be removed from the study, or treatment stopped by the Investigator for any of the following reasons:
 - Occurrence of CTCAE Criteria of grade 3 or higher that are deemed attributable to the transfusion per the opinion of the PI
 - PI decides to withdraw the subject due to noncompliance
 - Withdrawal by the PI or subject because of treatment side effects or complications

6.8 Key Definitions

- 1) *Vaso-occlusive pain crisis*: an episode of acute pain with no cause other than a vaso-occlusive event lasting at least 24 hours that requires the administration of oral or parenteral opioids in a medical facility.
- 2) *Acute Chest Syndrome*: an acute illness requiring medical facility attention characterized by fever and/or respiratory symptoms, accompanied by a new pulmonary infiltrate on a chest X-ray.
- 3) *Priapism*: an acute illness requiring medical facility attention characterized by *an* erect penis that does not return to its flaccid state, despite the absence of both physical and psychological stimulation, within four hours.
- 4) *Acute infection*: an acute illness requiring medical facility intervention (i.e. prescription of antibiotics or hospital admission) characterized by any subjective symptom.
- 5) *Chronic transfusion*: receiving red cell units on a 3-8 week schedule as part of routine, non-acute care).

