Adults with SCD may be uniquely susceptible to the deranged physiology of older units because they are prone to infections, inflamed and poorly equipped to handle excess red cells with high PS. Vaso-occlusion-induced tissue damage activates macrophages and leukocytes, which in turn leads to a chronic pro-inflammatory state.⁷²⁻⁷⁶ Reperfusion injury further exacerbates inflammation with the generation of reactive oxygen species as well as additional endothelial and leukocyte activation.^{77,78} Activated macrophages, leukocytes and endothelium then promote more vaso-occlusion in what becomes a vicious cycle of ischemia, injury and inflammation.⁷⁸ Intravascular hemolysis with release of cell-free hemoglobin and heme also contributes to this pathophysiology as cell-free hemoglobin is a sink for nitric oxide, a potent vasodilator and platelet antagonist,^{32-34,78} and heme activates endothelial cells via TLR4 receptors.^{35,36} Prior to penicillin prophylaxis, infection was the primary cause of death in patients with SCD due to splenic dysfunction.⁷⁹⁻⁸¹ The cumulative result of SCD's pathology is an adult who is prone to infections, chronically inflamed and susceptible to the pathology of PS-high, older red cells, and the consequent increased levels of cell-free hemoglobin, heme and NTBI in circulation. In fact, on sickle erythrocytes (not transfused cells) PS exposure is well-known to cause adhesion to the endothelium and thrombin generation, both of which worsen the pathology of vaso-occlusion.^{82,83} Since older red cell units with increased PS exposure can promote a similar physiology as SCD, they may exacerbate the illness of these vulnerable patients.

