10.2. Analysis Plan

The analysis will be an intent to treat (ITT) with all those randomized being included in the study. For all aims, the distribution of, and relationship between, variables will be explored with summaries, plots, and tree analysis. All statistical estimates of population parameters will be tabulated along with corresponding confidence intervals (CIs). All hypothesis tests yielding large p-value (e.g., $p > \alpha$) will be reported as being inconclusive. [name], the lead biostatistician, or her designee, will perform these analyses. Where necessary for parametric assumptions, appropriate transformations will be employed with justification for their use; otherwise, non-parametric tests will be used. P-values will be reported without dichotomization wherever applicable. Data obtained from transfusion events where units of the appropriate age could not be obtained (study deviation) will be excluded from a subanalysis of the dataset, and the same distribution of, and relationship between, variables will be explored with similar summaries, plots, and tree analysis as in the ITT analysis. All subjects, regardless of age and gender, will be analyzed together as one cohort. Statistical software used in this study will be Cytel, StatXact and LogXact, SAS version 9.4, and Salford systems CART (Classification and Regression Trees). To adjust for multiple comparisons, we will use the false discovery rate approach which is less conservative than the Bonferroni approach. *Missing data:* Logistic regression will be used to investigate the possible causes for missing data and to investigate if data are missing at random (MAR). Reasons for missing data will be documented in the study database. We do not anticipate any missing data or drop-outs, but we will monitor these events. Assuming data are MAR, multiple imputations will be used for items, and for repeated measures, a random effects models will be used; the structure for the variance covariance matrix will be explored under the constraints of sample size. A sensitivity analysis will also be performed to evaluate the robustness/fragility of the study's main results to reasonable perturbations of the statistical methods and assumptions used. Results of the sensitivity analyses will only be used to guide trust in the main results.

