The primary outcome measure is the change in CD62L (activated) circulating monocyte/macrophage MFI at 2 hours post-transfusion compared to the subject pre-transfusion. We will compare the two groups (\geq 30 day-old compared to \leq 10 day-old unit exposure) using a two sample two-sided t-test of the log at an alpha of 0.05. Power: We will have at least 80% power to detect a change in the ratio of 1.35 post-transfusion if the variability is similar to that seen in our preliminary data.

Exploratory: We will use a general(ized) linear model to include biochemically old units transfused (Aim 1 outcome), regardless of unit age, as a covariate in our analysis. Other co-variates in this model will include free heme, cell free hemoglobin, and NTBI. We will similarly compare other obtained activation measures as outcomes: activation markers for monocytes, neutrophils (as listed in section 6) and measured plasma cytokine

concentrations (section 6). We will also plan for auxiliary analyses of the outcome variables in which the explanatory variable is the age (days) of the RBC units --to characterize the degree to which age (days) can accurately predict the clinical and physiologic outcome measures defined. Lastly, as an exploratory aim, we will evaluate the *in vivo* change in recipient red cell PE/PS positivity at 2 and 24 hours post transfusion.

Aim 3:

The primary outcome variable is the rate of post-transfusion infections in the patient. The primary estimand is the treatment effect defined as the difference between the regimen-specific proportions of patients in the target populations that would experience post-transfusion infections. This population parameter will be estimated as a function of the proportions observed in the sample of patients studied. The point estimate will be reported along with the corresponding 95% confidence interval estimate. The presence of an indwelling catheter will be used as a key co-variate in this analysis. *Power:* A difference of 20% will be of clinical interest. We do not expect to have adequate power for this pilot study but at an alpha of 0.05 with 20 subjects in each group we will be able to detect a difference of 47% between the proportions.

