Exploratory: We will explore the relationship of blood age and transfusion of biochemically old red cell units on the change in Hb and HbS% over time, daily pain scores (0-10 as an ordinal scale), opioid use and dose, ED and hospitalization rate, infection symptoms, new alloantibody formation, and antibiotic use during the 3-month study period. We will compare groups using a Fisher exact test. We will also plan for auxiliary analyses of the outcome variables in which the explanatory variable is the age (days) of the RBC units --to characterize the degree to which age (days) can accurately predict the clinical and physiologic outcome measures defined.

AIM 4:

We will calculate the mean, median, minimum, and maximum levels of each metabolic compound analyzed by [name] in his laboratory at the University of Colorado. Analysis tools and methods will be determined by his research team, and will focus on changes in the patient and the unit pre and post transfusion.

AIM 5:

Feasibility Analysis: We will assess important variables necessary to develop a future larger clinical trial on this subject. Areas that we will investigate during the course of this trial will include frequency and content of missing data, subject drop out rates, and estimates of outcome measure precision. For this study, we will evaluate the number of males, females, and adolescents that enroll in the study to inform future studies. We do not expect there to be differences in the key outcomes based on these variables, and plan to analyze all 40 subjects together as one cohort, but differences by age and gender will be evaluated and considered.

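### The acute infection definition behind the Aim 3 primary outcome requires no evidence of infection, so as written an admitted pain crisis also qualifies

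*Combined protocol and SAP*

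**What the plan says.** Section 6.8, item 4 defines acute infection as "an acute illness requiring medical facility intervention (i.e. prescription of antibiotics or hospital admission) characterized by any subjective symptom". The two interventions are joined by *or*. No site, organism, fever, imaging or clinician diagnosis is asked for, and no sickle cell event is excluded.

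The neighbouring items each name a distinguishing feature. Item 1, pain crisis, is "an episode of acute pain with no cause other than a vaso-occlusive event", lasting at least 24 hours and needing opioids in a medical facility. Item 2, ACS, is "an acute illness requiring medical facility attention characterized by fever and/or respiratory symptoms, accompanied by a new pulmonary infiltrate on a chest X-ray".

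For Aim 3, section 10.2.1 states: "The primary outcome variable is the rate of post-transfusion infections in the patient". It gives no case definition and does not cite 6.8, but the documents contain no other definition of infection.

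Three other places bear on the point:

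- Section 6.3 has the coordinator record "Subject ED and hospitalization events, and etiologies". It points to definitions in 6.7, although they stand in 6.8.
- Section 8.6 has the DSMB count subjects with a clinically documented infection leading to an ED visit or admission. Section 9 treats serious infection and pain crisis as two outcomes.
- The Aim 3 exploratory list in 10.2.1 includes daily pain scores, "opioid use and dose, ED and hospitalization rate, infection symptoms" and antibiotic use. It does not split ED and hospital visits by recorded etiology.

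**The concern.** A primary outcome called infection should count infections. Under item 4, admission for any acute symptomatic illness counts. In this population a common alternative reason for admission is the underlying disease itself: part of the UNC chronic transfusion group is transfused for chronic pain (section 1, Preliminary Studies).

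Vaso-occlusive events are also a possible effect of the treatment under test. The background section argues that older units "can promote a similar physiology as SCD, they may exacerbate the illness of these vulnerable patients". So the events that could be miscounted may differ by arm.

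Two errors follow if the rule is applied literally. Equal background admissions would dilute a true infection effect. Unequal ones would show a vaso-occlusive effect under the infection label. Section 2.1 says the study is to inform a larger trial, whose designers need to know which of the two was seen.

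**Working it through.** **1. Which events meet item 4.** Its elements are an acute illness, any subjective symptom, and antibiotics or admission.

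- *Admitted pain crisis:* acute, symptomatic, admitted. All elements are met.
- *ACS admitted without infection:* acute, symptomatic, admitted. All elements are met.
- *Pain crisis treated without admission or antibiotics:* not met.

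Item 1's exclusion runs one way. It keeps other causes out of pain crisis, but item 4 has no matching clause to keep pain crises out of infection.

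**2. The plan's own figure.** Section 10.2.1 gives a detectable difference of 47 points for Aim 3, with 20 per arm and alpha 0.05. Neither power nor comparator rate is stated there. I assume 80% power (as for Aim 1) and a two-sided Fisher exact test, enumerated in full. Power for a 47-point difference is 87.0%, 83.1% and 79.5% at comparator rates of 10%, 15% and 20%, with a minimum of 77.3% near 26.5%. The figure reproduces at a comparator rate of about 20% and is not in dispute.

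**3. Dilution.** Let q be the infection risk and a the risk of a non-infectious admission, independent of infection. The documents give neither, so all values below are assumptions.

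- Counted proportion = 1 − (1 − q)(1 − a).
- With equal a in both arms, counted difference = (1 − a) × true difference.

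For the 20-point difference of clinical interest:

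| a | 5% | 10% | 20% | 30% | 40% |
|---|---|---|---|---|---|
| Counted difference (points) | 19 | 18 | 16 | 14 | 12 |

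Fisher power at 20 per arm for a true 47-point difference:

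| True infection risks | a = 0 | a = 10% | a = 20% |
|---|---|---|---|
| 5% v 52% | 92% | 75% | 56% |
| 10% v 57% | 87% | 71% | 54% |
| 20% v 67% | 80% | 66% | 55% |

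Example for 10% v 57% with a = 20%: 1 − 0.90 × 0.80 = 28.0% and 1 − 0.43 × 0.80 = 65.6%, a difference of 37.6 points = 0.80 × 47.

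**4. False difference.** Set infection at 10% in both arms, with non-infectious admissions at 20% in one arm and 30%, 40% or 50% in the other. The counted proportions are 28% v 37%, 46% or 55%, so differences of 9, 18 or 27 points appear with no infection effect. With infection at 5% they are 9.5, 19 and 28.5; with 20%, they are 8, 16 and 24.

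**5. One patient.** Each patient counted only because of a non-infectious event moves an arm of 20 by 1/20 = 5 points.

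Steps 3 and 4 assume that every such admission is coded as infection. If infections and crises fall in the same patients, the effects are smaller.

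**The case against.** The strongest reply is that nobody would code this way. The item is headed acute infection, section 6.3 asks for etiologies, and assigning an etiology means naming a cause. A coder would have to find that pain had no cause but vaso-occlusion and then label the same event an infection. Sections 8.6 and 9 and the phrase clinical infections in the 10.2.1 variable list show that the plan means the two to be distinct. This stands as to intent: miscoding is possible, not shown. It does not repair the rule, which is the only one supplied and says something else.

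A reader might infer that section 10 offers no means of telling a vaso-occlusive signal from an infectious one. The documents do not support that. Pain scores, opioid use, infection symptoms and antibiotic use are all listed, and a purely vaso-occlusive effect should move the first two more than the last. The gap is narrower: the visits themselves are not split by etiology. The sensitivity analysis in 10.2, covering "reasonable perturbations of the statistical methods and assumptions used", does not name the event definition.

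A reader might also infer that safety monitoring is compromised. It is not, on this point: 8.6 has its own infection wording and compares pain admissions too.

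Finally, counting antibiotic-treated ACS is defensible. Pneumonia made up 6 of the 13 preliminary infections (6+2+2+1+1+1) and overlaps with ACS. This also stands, and it limits how strict the remedy should be.

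**Conclusion.** The concern holds as a defect in a stated rule. Item 4 admits events that the rest of the plan treats as something other than infection, and the Aim 3 primary outcome has no other definition to rest on.

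Its size cannot be established. The dilution factor (1 − a) is exact under independence and equal risk, but a is unknown, and the false differences of 9 to 27 points need both unequal admission risks and literal coding. None of these figures is a prediction.

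Severity is minor. Sections 2.1 and 10.2.1 describe a feasibility study without adequate power for Aim 3, so no confirmatory conclusion depends on this. What is at stake is whether the Aim 3 estimate can be read as an infection effect when the larger trial is designed.

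**What to change.** Add to section 6.8, item 4: *and an infection diagnosed and documented by the treating clinician (with site or organism where known); an event meeting the pain crisis, ACS or priapism definition counts only if such an infection is also documented.* Classify events blind to arm, from the etiologies already recorded under 6.3.

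If the definition cannot change because 15 subjects are already enrolled, keep it and apply the criterion as a named Aim 3 sensitivity analysis in section 10.

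The cost is one clause, or a sentence or two in section 10, plus the blinded classification of a small number of events. Section 4.3 already withholds arm and unit age from staff who collect data, and no new data collection is planned. The downside is that, because ACS and pneumonia overlap, some true infections may be removed when the record does not name one.
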